6.3.2 Breathlessness, Cough, and Sputum Scale (BCSS)

 All participants will be assessed using the validated Breathlessness, Cough, and Sputum Scale at baseline and follow-up as a generic measure of their symptom burden. We will compare the differences between participants at baseline and follow-up and correlate this to their HROM findings.

6.3.3 Medical Research Council (MRC) Dyspnoea Scale

 All participants included in this trial will have a baseline and follow-up MRC dyspnoea scale recorded.

6.3.4 Visual Analogue Scales (VAS) – Cough severity

- All participants will be asked to complete a VAS assessment at baseline and follow-up, and repetitive VAS measures through the use of a physical 'cough diary' while being monitored with the Hyfe Cough Tracker. This records the participants' assessment of cough severity on a 100mm linear scale ranging from 'no cough' (0mm) to 'worst cough imaginable' (100mm). We will ask participants to complete a cough severity VAS tool daily for the duration of the study.

6.3.5 COPD Assessment Test (CAT)

- All participants whose primary respiratory diagnosis is COPD will be assessed using the CAT at baseline and at follow-up. This is an 8-item questionnaire which aims to quantify the symptom burden of patients with COPD and how this impacts their life.

6.3.6 Asthma Control Questionnaire (ACQ)

- All participants whose primary respiratory diagnosis is asthma will be assessed using the ACQ at baseline and at follow-up. This is a 7-item questionnaire that aims to assess the symptomatic control of patients with asthma.

6.3.7 Numerical Rating Scale – Breathlessness Severity

- All participants will be asked to complete a numerical rating scale of their breathlessness at baseline. This will be a horizontally arranged scale numbered 0-10, with 0 representing no breathlessness and 10 representing the worst breathlessness imaginable.

6.4 Disease Specific Health Status and Quality of Life

6.4.1 Leicester Cough Questionnaire (LCQ)

- All participants with a primary respiratory diagnosis of chronic cough will be assessed using the LCQ at baseline and at follow-up. This 19-item questionnaire uses a 7 point Likert scale to assess the impact of cough on the physical, social, and psychological welfare of the patient.

6.4.2 St. George's Respiratory Questionnaire

All participants will be assessed using the short-form SGRQ at baseline and at follow-up. This 40-item questionnaire is aimed to measure impact on overall health, daily life, and perceived well-being in patients with obstructive airways disease.

6.4.3 King's Brief Interstitial Lung Disease Questionnaire

All participants with a primary respiratory diagnosis of interstitial lung disease will be assessed
using the KBILDQ. This is a 15 item 7-point Likert scale questionnaire aimed to measure the
impact of ILD on quality of life and health status. Measurements will be taken at baseline and
follow-up.

6.4.4 Cystic Fibrosis Questionnaire

All participants with a primary respiratory diagnosis of cystic fibrosis will be asked to complete a CFQ at baseline and at follow-up. This is a 50-item questionnaire aimed to assess the overall health, daily functioning, and wellbeing of patients with cystic fibrosis.

6.5 Continuous cough monitoring using the Hyfe Cough Tracker

The Hyfe Cough Tracker is a wellness information tool (artificial intelligence-based software for smartphones or wearable devices, such as smartwatches) to objectively, continuously and passively monitor cough. The app captures, records and processes only 0.5s sound snippets after some explosive sound is detected that is greater than a set threshold above background noise signal. This period of time is enough for the artificial intelligence cough classifier to determine if the sound was a cough or not, and not enough to discover some personal data out of this 0.5s sound snippet, therefore allowing for continuous cough monitoring and preserving privacy. Such sound snippets, classified as "cough", are stored in a secure server and made available for the investigator playback. Each sound recording includes a time stamp and, if users enable location sharing, a GPS coordinate. Daily cough counts, their dynamics (diurnal variation, mean counts, among other) and sound playbacks are available for the investigator on a web-based dashboard. The dashboard only displays anonymised data as every participant receives a

dedicated Hyfe ID, which is only known to the investigator, and not for the staff at Hyfe.

We will assist in setting up the Hyfe Cough Tracker equipment and hand out dedicated devices with the application (to be determined - either a dedicated smartphone, or a smartwatch) to the study participants who provide separate consent to record cough sounds over at least a 7-day period prior to azithromycin initiation. Participants will then be asked to "wear" the cough recording device in between the two study visits.

The captured data from the Hyfe Cough Tracker will be accessible by the investigator at any time through the web-based, secure dashboard and will be used to share objective cough dynamics with the participants on their visits.

Basic, non-identifiable demographic information will be shared with Hyfe (with participant consent), including sex, year of birth, respiratory diagnosis, and date of testing.

7.1 Participant Recruitment and Consent

Potential participants will be identified from the Hull University Teaching Hospitals NHS Trust respiratory medicine outpatient department. Participants will be eligible for screening if their usual treating clinician feels it appropriate to initiate long-term azithromycin treatment as part of their usual NHS care. Patients can be included in the trial if they have already undergone HROM investigation in the past 3 months prior to identification and are being initiated on long-term azithromycin treatment, however patients cannot have been taking azithromycin at the time of their previous HROM investigations.

All participants will be given adequate time to consider the trial and formulate questions. Any questions will be addressed and answered fully by the PI or delegated trial doctor. An actual period is not specified. All potential participants will be given a Participant Feedback Questionnaire to complete and return.

The PI retains overall responsibility for obtaining informed consent of participants at site and must ensure that any person delegated responsibility to participate in the informed consent process is duly authorised, trained and competent to participate according to the ethically approved protocol, the UK clinical trial regulations, GCP and the Declaration of Helsinki.

Only delegated trial doctors will be allowed to take consent in this study. All consent forms will be completed and stored in accordance with local ethics and general data protection regulation requirements.

7.2 Screening for Eligibility

A Participant Screening Log will be kept of all potentially eligible participants including the reasons for non-entry and/or non-approach, if applicable by all the study team.

An initial screening assessment will be undertaken prior to signing the informed consent form to ascertain that the participant may be potentially suitable for the trial and can be approached. Only eligible, consenting participants will proceed to undertake trial measures as outlined in Section 7.3.

The plan of management will be checked with the potential participant's usual treating physician to identify any planned or expected change to management during the trial period that may impact trial participation.

Participants identified as being potentially suitable for entry into the trial and who are approached about the trial and have given consent will undergo a review of eligibility criteria and complete eligibility screening.

Information about eligibility will be obtained from discussion with the potential participant and review of the participant's medical record.

7.3 Screening Visit (Day -28 to -7)

Suitable participants who have been identified on specialist assessment by the HUTH respiratory medicine department or the trial team will be screened for eligibility and will obtain informed consent if eligible. If the participant agrees to take part in the study, they will undertake screening. The following procedures will be performed during this visit:

Eligibility Assessment:

- Review of inclusion and exclusion criteria
- Consent if eligible
- Participant invitation experience questionnaire*
- Hull Airway Reflux Questionnaire
- Set up of the Hyfe Cough Tracker© device
- Cough VAS

7.4 Baseline Assessment Visit (Day 0)

Participants will be invited to attend the Respiratory Medicine Clinical Trials Unit at Castle Hill Hospital for baseline assessment visit within 1 month of screening. Participants who have not had an HROM performed within 3 months prior to screening will also undertake their initial HROM investigation during this visit.

Baseline Assessments:

- Medical history
- Review of previous laboratory results (provided they have been performed as part of routine clinical care in the 3 months prior to recruitment):
 - o Blood Haemoglobin level
 - Total blood white cell count
 - Total blood eosinophil count
 - Blood alanine transaminase
 - Blood alkaline phosphatase
 - Blood bilirubin level
 - o Blood albumin level
 - Sputum microscopy, culture, and sensitivity results.
- Physical examination
- Monitoring of vital signs
- Weight and height
- Electrocardiogram
- Spirometry
- BSCC
- HARQ
- MRC Dyspnoea Scale
- St George's Respiratory Questionnaire
- Disease-specific symptom questionnaires
- Disease-specific quality of life questionnaires
- Cough Visual Analogue Scale
- Monitoring of cough frequency using the Hyfe Cough Tracker
- Initial HROM investigation as per the HROM protocol in section 6, performed by a clinical scientist specialising in GI physiology.

*All individuals undergoing screening will be asked to complete an anonymous survey ('Invitation Experience Survey':) whether they consent to take part in the trial or not. If participants agree to complete the questionnaire this will be taken as implied consent for the information they provide in the survey to be used for the purposes of this study. This survey will be completed with the help of a member of the trial team and stored in the site file.

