3. TRIAL DESIGN

A prospective observational trial evaluating the effect of 1 month (up to 6 weeks) of azithromycin treatment on oesophageal motility and symptom burden in patients with chronic respiratory disease who are being commenced on azithromycin as part of routine clinical care. Participants will be investigated using HROM before and during treatment with azithromycin to evaluate the change in oesophageal function.

The trial team will not be prescribing the azithromycin treatment for the participants, as this will be the decision and the responsibility of their usual treating clinician. However, it is anticipated that all participants will be treated with azithromycin 250 milligrams once daily or three times per week throughout the duration of the study. The acceptability of HROM as a diagnostic tool will be assessed through participant experience surveys. We will also analyse other feasibility outcomes such as eligibility to recruitment ratio and participant retention rate to ascertain how willing participants will be to engage in all trial procedures to inform larger clinical trials/ mechanistic studies.

Participants will be investigated with validated questionnaires to ascertain their symptom burden before and during treatment with azithromycin. With this information we will correlate changes in oesophageal function and symptom burden in this group of patients. Participants will also be asked to use the Hyfe Cough Tracker© equipment (to be further determined - if a dedicated smartphone running the application or a wearable smartwatch running the application) for at least one week prior to their initiation of azithromycin and for the duration of their azithromycin treatment whilst in the trial. We will then observe the difference between daily cough counts before and after azithromycin treatment and be able to ascertain how this correlates with oesophageal function. Additionally, we will look into the relationship of objective cough frequency data and repetitive subjective cough evaluation using cough VAS.

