4.3 Participant Identification and Screening

All patients attending the Hull University Teaching Hospitals NHS Trust (HUTH) respiratory medicine outpatient department for management of their chronic respiratory disease and are being considered for long-term treatment with azithromycin will be considered suitable for participation. Respiratory medicine clinicians and specialist nurses working within the trust will be trained and instructed in the recruitment procedure and any patients who may meet the eligibility criteria will be referred to the trial team and contacted, with the patients' consent and after given time to consider participation and ask questions, for screening to assess eligibility to participate in the study.

Participants expressing an interest in the trial will be provided with a participant information sheet and informed consent will be obtained. All eligible patients who are approached for the trial will be invited to complete a short anonymous questionnaire (Appendix: Trial Invitation Experience Survey) assessing their experience of recruitment and why they consented to participate or declined.

Participants that fail screening can be re-screened (to a maximum of 3 times) if the reason for screen failure is resolved prior to completion of trial recruitment. Participants entering the trial following re-screening after an earlier failed screening will be allocated a new trial ID and have their earlier trial ID and the reason for initial screen failure recorded in their CRF and the Participant Master Index.

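### The invitation survey is called anonymous, yet by default a member of the trial team helps the patient complete it, which puts the reasons for accepting or declining at risk of social-desirability bias

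*Protocol*

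**What the plan says.** Section 4.3 introduces the survey: "All eligible patients who are approached for the trial will be invited to complete a short anonymous questionnaire". It gives the content as "assessing their experience of recruitment and why they consented to participate or declined".

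The schedule of assessments and section 7.3 place the survey at the screening visit. Its footnote, printed at the end of section 7.4, again calls it anonymous, extends it to everyone screened whether or not they consent, and treats completion as implied consent to use the answers. The footnote then says: "This survey will be completed with the help of a member of the trial team and stored in the site file".

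On who the trial team is, section 4.3 says that "any patients who may meet the eligibility criteria will be referred to the trial team and contacted", and section 7.1 says "Only delegated trial doctors will be allowed to take consent in this study".

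Section 7.1 also states: "All potential participants will be given a Participant Feedback Questionnaire to complete and return". That questionnaire name appears nowhere else in the protocol.

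On use of the results, section 3 says: "The acceptability of HROM as a diagnostic tool will be assessed through participant experience surveys". Section 6.1 makes feasibility and acceptability the primary outcomes. Sections 4.4 and 7.5 describe a separate, later Trial Experience Survey for those who complete or withdraw. It too is anonymous, and no staff help is stated for it.

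**The concern.** The survey asks patients to rate how they were recruited and to say why they agreed or refused. The person helping belongs to the team whose recruitment is being rated. Patients in that position may soften criticism or choose a neutral reason over a frank one. Because completion counts as implied consent, the description of the survey as anonymous should also be accurate.

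What is at stake is the information on reasons. Section 3 wants the feasibility results to show how willing people are to undergo all trial procedures, in order to inform larger studies. Patients unwilling to have HROM fall under an exclusion criterion in section 4.2 and never reach the Trial Experience Survey. The invitation survey is the only listed survey that asks decliners why. The other record of reasons for non-entry, the screening log in section 7.2, is kept by the study team and is no independent check.

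**Working it through.** No figure in the protocol is in dispute and no formula applies. The check sets the statements on the survey side by side.

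1. **Anonymity against mode of completion.** Sections 4.3 and 7.4 both say anonymous. The section 7.4 footnote says a trial team member helps, and states this for the survey as a whole, without limiting it to patients who ask or need help. A form without a name can be anonymous once filed. The answers are still not anonymous to the team when they are given. Read as a promise to the respondent, the two statements conflict.

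2. **Who the helper is.** The trial team contacts referred patients (section 4.3), and delegated trial doctors take consent (section 7.1). The protocol does not say that the helper is the same individual who approached or consented the patient. It does say that the helper comes from the same team, and nothing keeps the roles apart.

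3. **Storage.** The completed survey goes to the site file. Section 13.2 keeps the original signed consent forms in the Investigator Site File. If this is the same file, surveys and identifiable forms from a study of 30 participants sit together. This matters only if the survey carries, or can be matched to, an identifier. The form itself is not shown.

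4. **One form or two.** Section 7.1 gives out a Participant Feedback Questionnaire to be completed and returned. The schedule lists two surveys only: Invitation Experience at screening and Trial Experience at follow-up. The second is for those who complete or withdraw, so the invitation survey is the closest match for a form given to potential participants. Either one form has two names, or there is another form that the schedule does not list. The text does not say which.

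5. **Who receives it.** There are three definitions:
   - Section 4.3: eligible patients who are approached.
   - Section 7.1: all potential participants, if this is the same form.
   - Section 7.4: all individuals undergoing screening.

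   These need not be the same people. A patient excluded at screening for being unwilling to have HROM is covered by 7.4 but, being ineligible, is arguably not covered by 4.3. A patient who refuses on first contact may be covered by 4.3 but not by 7.4. The choice decides which decliners are heard.

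6. **Link to the outcomes.** The recruitment outcomes in section 6.1 (eligibility-to-consent ratio, recruitment rate, retention) are counts and do not depend on how the survey is filled in. The HROM acceptability outcome is the proportion of participants who find the investigations acceptable. The invitation survey is given at screening, before the baseline visit at which the trial HROM is done unless a recent one exists, and decliners are not participants. The Trial Experience Survey is therefore the more natural source. Section 3 speaks of experience surveys in the plural, so some contribution from the invitation survey cannot be ruled out.

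7. **Size and direction.** The protocol gives no expected refusal rate, no distribution of reasons and no data on assisted against unassisted completion. Neither the size nor the net direction of any bias can be computed.

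**The case against.** The strongest reply is that no listed outcome depends on the stated reasons. The recruitment outcomes are counts, and HROM acceptability will come mainly from a later survey with no stated help. This largely stands, and it limits the point to the supporting information on why patients accept or decline.

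A second reply is that help can raise response and completeness, so unassisted return may trade one bias for another. This is fair. It is a reason to keep help available on request and to have the form completed at the visit.

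A third is that the helper might not be the person who recruited the patient, and that filing a form without identifiers does not break anonymity. Both are possible, but the protocol secures neither, and the helper is still a member of the team being rated.

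Three stronger readings are tempting and are not supported:
- A reader might infer that the reasons will be biased, or that HROM acceptability will be inflated. The text supports a risk only, and it does not mention fear of HROM as a reason for declining.
- A reader might infer that sections 7.1 and 7.4 contradict each other on the mode of completion. The names differ, and a patient could be helped to complete a form and then return it. This is an ambiguity to resolve.
- A reader might want to attach a percentage to the softening of answers. Any such figure would be invented.

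**Conclusion.** The point holds in a limited form. The protocol promises anonymity and then makes completion with trial team help the default, so the team whose recruitment is being rated learns the answers. That is an internal contradiction on the face of the text, and it creates a credible risk of social-desirability bias in the reasons for consenting or declining. The effect on the primary HROM acceptability proportion is probably limited.

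This rests on two readings: that the footnote describes the standard mode, as it is written, and that the Trial Experience Survey is the main source for the acceptability proportion. The matter is minor, but it is cheap to put right and is fixed in the protocol body, so a statistical analysis plan would not resolve it.

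**What to change.** - Replace the footnote sentence in section 7.4. Patients complete the survey privately at the visit and return it in a sealed envelope or box, with no identifiers on the form.
- Offer help only on request, where possible from someone who did not approach that patient, and add a tick box for when help was given, so that assisted and unassisted forms can be told apart.
- State whether the Participant Feedback Questionnaire in section 7.1 is the same form. If it is, use one name. If it is not, add it to the schedule.
- Use one definition of who receives the survey in sections 4.3, 7.1 and 7.4, and make clear whether it includes patients who refuse on first contact and those excluded for unwillingness to have HROM.

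The cost is wording and envelopes. The downside is that somewhat fewer or less complete forms may come back. Completion at the visit and help on request should keep that loss small.

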7.5 Follow-up Visit (Day 28 to 42)

Participants will be asked to attend for follow-up assessments at 28-42 days after initiation of azithromycin therapy. The participants will undertake a full follow-up assessment and will also have a full review of their condition, including healthcare utilisation, side effects from azithromycin treatment, and experience of HROM investigation.

Follow-up assessment:

- physical examination
- Vital signs
- Electrocardiogram
- Spirometry
- BSCC
- HARQ
- MRC Dyspnoea Scale
- St George's Respiratory Questionnaire
- Cough Visual Analogue Scale
- Disease-specific symptom questionnaires
- Disease-specific quality of life questionnaires
- Monitoring of cough frequency using the Hyfe Cough Tracker©
- Follow-up HROM investigation as per the HROM protocol in section 6, performed by a clinical scientist specialising in GI physiology.
- SAE/ AE reporting
- Health care utilisation recording
- Evaluation of usual care received
- Trial experience survey

